8.2 CRFs completion

The information requested on CRFs are to be recorded by writing with pen on paper printed CRFs.

- The principal investigator is responsible for the completeness and accuracy of the information transcribed on the printed CRF forms.
- No field will be left incomplete without a reason.

8.3 Data entry, analysis and storage

All printed CRFs number 1-7, fully completed and signed in original, must be grouped together in one folder per patient. The original completed CRFs will be stored by the principal investigator in a specific study file, for a period of 15 years at the study centre. A copy of the completed CRFs will be stored by the sponsor in a specific study file, for a period of 15 years at the sponsor facility. Principal investigator and sponsor have the responsibility for data management. The CRF data will be entered by the sponsor into a single electronic database protected by password, which will undergo periodic back-up after each new data entry. The sponsor will have the responsibility for data analysis. At the end of the study, a PDF/A copy of the database file will be stored at the sponsor server and, moreover, will be saved on CD and other external memory and stored at the sponsor facility.

9. Duration of the study

The study will begin following the Ethics Committee approval and after the authorization from the C.O.Q. Management to start the study. A duration of approximately 12 months is estimated for patient screening, telephone contact, follow-up visits and data recording. The study will end with the completion of all the forms required for all enrolled patients. The duration of data entry from the paper CRF format to the electronic database is approximately 1 week but can be carried out at the same time as data collection. An additional 2 months are estimated for data analysis and drafting of the study report.

10. Statistical analysis

10.1 Sample size

In order to calculate the sample size of the study group and the control group, a non-inferiority study is chosen as the most suitable type. Since in the medium term (5-7 years of follow-up), there is reasonably no expectation of significantly better survival results when using a vitamin E polyethylene articular insert compared to a standard polyethylene insert, but rather comparable results. Therefore, we choose to calculate the sample size of the groups using a statistical test of non-inferiority for binary variables (failed implant vs survived implant) of 2 paired groups.

From the prosthetic joint replacement registries of Australia and UK, reports of 2019 and 2018 respectively, the cumulative percentage of revision in total knee arthroplasty with mobile insert is reported as 2.77% at 5 years of follow-up [NJR Report 2018] and 2.8% for HXPE polyethylene inserts at 5 years of follow-up [AUS Report 2019]. The Australian registry also reports 2.3% as the cumulative revision rate for total knee arthroplasty with an insert supplemented with vitamin E at 5 years of follow-up. A difference of at least 4% is considered clinically relevant between survival rates of different knee implants.

Using these failure/survival rates for the control group and the treatment (vitamin E) group, choosing a significance level (alpha) of 5%, a power of 80%, a survival rate of 97.2% for the control and 97.7% for the vitamin E group and with 4% as margin of non-inferiority between both groups, the calculation provides 152 implants per group.

<https://www.sealedenvelope.com/power/binary-noninferior/>

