Co-investigators:	
• [name] - Director of the Complex Structure Unit 1 Orthopaedics and Traumatology, Città della Salute Hospital / CTO of Turin, Italy.• [name] - 1st level Medical Director of Unit 1 Orthopaedics and Traumatology, Città della Salute Hospital/CTO of Turin, Italy and Cardinal Massaia Hospital, Asti, Italy.
Sponsor contact person:	[name] – Clinical Research Manager at Permedica S.p.A.
Study rationale	The clinical evidence for outcomes after primary total knee arthroplasty with vitamin E polyethylene is still scarce in the short term and published clinical studies on vitamin E polyethylene total knee arthroplasty with medium term results are lacking.
Objective	The aim of the study is to investigate on the survival rate and mid-term clinical and radiographic results of a consecutive series of primary total knee arthroplasty performed using a cemented total knee prosthesis with a mobile insert in polyethylene with vitamin E, comparing them with the same implant with a mobile insert in conventional polyethylene.

Primary endpoint	Cumulative implant survival with revision for aseptic loosening as the end-point.
Secondary end-points	Cumulative implant survival with revision for any reason as the end-point. Reinterventions and non-surgical complications Forgotten Joint Score (FJS-12). America Knee Society Score (Knee / Function). Radiographic signs of radiolucencies and osteolysis.
Study group	Minimum 152 total knee arthroplasties with vitamin E polyethylene insert.
Control group	Minimum 152 total knee arthroplasties with the same implant but with conventional polyethylene insert without vitamin E.
Medical device	GKS Prime Flex Mobile Bioloy, cemented TiNbN-coated mobile bearing knee prosthesis by Permedica with vitamin E polyethylene (VitalE®) or conventional polyethylene rotating ultra-congruent tibial insert.
Inclusion criteria	
 Patient who received primary total knee arthroplasty with GKS Prime Flex Mobile Bioloy by Permedica with vitamin E polyethylene or conventional polyethylene insert. Minimum follow-up of 7 years. Patient aged \geq 18 years and $<$ 85 years. Patients who signed the informed consent.

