4.1 Primary endpoint

The primary objective of the study is to verify that the survival of the prosthetic implant with vitamin E polyethylene is not inferior to the survival of the prosthetic implant with conventional polyethylene. The primary endpoint is therefore the cumulative implant survival, defining revision for aseptic loosening as the endpoint (or failure).

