4.2 Secondary endpoints

The secondary objectives of the study are survival for any reason, clinical results and radiographic results, prevalence of complications. Secondary endpoints are therefore:

- Survival of the prosthetic implant with vitamin E polyethylene and with conventional polyethylene, with revision for any reason as the end-point,
- the American Knee Society Score (KSS) with Knee score and Function score,
- the Forgotten Joint Score (FKS-12),
- Number of reinterventions (without any component removal), non-surgical complications and adverse events,
- Periprosthetic radiolucent lines and radiographic signs of periprosthetic osteolysis.

5. Prosthetic device

The medical device under investigation is a cemented bicompartimental knee prosthesis with a rotating tibial plateau, the GKS Prime Flex Mobile Bioloy® by Permedica S.p.A. (Figure 1). The femoral and tibial components are both coated with a titanium-niobium nitride (TiNbN) ceramic coating with 4.5 ± 1.5 microns thickness (Bioloy®). The femoral and tibial component are both cemented. The rotating tibial insert has an ultra-congruent articular surface and is made with

UHMWPE blended with vitamin E (0.1% alpha-Tocopherol), non-cross-linked and sterilized by ethylene oxide (VitaE®), or with conventional non-cross-linked UHMWPE (Figure 2).

Figure 1. Cemented mobile-bearing total knee prosthesis with TiNbN coating, GKS Prime Flex Mobile Bioloy® by Permedica S.p.A.

[figure not shown]

Figure 2. A: UHMWPE blended with 0.1% vitamin E, non-cross-linked and ethylene oxide sterilized (VitaE®) ultra-congruent rotating insert. B: Conventional, non-cross-linked, E-beam sterilized UHMWPE ultra-congruent rotating insert with same design.

6. Study population

The study will concern a consecutive series of patients who underwent primary total knee arthroplasty with the same knee prosthesis at the C.O.Q. hospital in Omegna (VB), Italy, from January 2011 to December 2015 and who will meet all eligibility criteria.

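### The 80% power for 152 implants per group comes from 5-year revision rates with no stated cause, so neither it nor the 4-point margin is established for the primary endpoint, revision for aseptic loosening

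*Combined protocol and SAP*

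**What the plan says.** The synopsis gives the primary endpoint as "Cumulative implant survival with revision for aseptic loosening as the end-point". Section 4.1 sets a non-inferiority objective and repeats the definition: "The primary endpoint is therefore the cumulative implant survival, defining revision for aseptic loosening as the endpoint (or failure". Section 4.2 lists implant survival "with revision for any reason as the end-point" as a secondary endpoint, so the protocol itself treats the two events as different. Section 6.3 requires at least 7 years of follow-up.

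Section 10.1 takes its rates from two registries. For the control group it reports that "the cumulative percentage of revision in total knee arthroplasty with mobile insert is reported as 2.77% at 5 years of follow-up", and also "2.8% for HXPE polyethylene inserts at 5 years of follow-up". For vitamin E inserts it gives 2.3% at 5 years. No cause of revision is attached to any of these figures. The margin rests on one sentence without a source: "A difference of at least 4% is considered clinically relevant between survival rates of different knee implants". The calculation then uses "a survival rate of 97.2% for the control and 97.7% for the vitamin E group and with 4% as margin of non-inferiority", an alpha of 5% and a chosen power of 80%, and arrives at 152 implants per group. Sections 6.1 and 6.2 set that number as the minimum for each group.

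Section 10.2 plans Kaplan-Meier survival with 95% confidence intervals and a log-rank test at p < 0.05. It does not mention the margin.

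**The concern.** A reader will take 152 per group at 80% power as the operating characteristic of the primary comparison. It was computed for a different event (revision with no stated cause) at an earlier time (5 years rather than 7 or more). No aseptic-loosening rate appears in the documents at any time point, so the reader cannot convert one into the other.

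The margin matters more than the power. A tolerance of 4 percentage points is judged against the rate of the event to which it applies. If loosening accounts for only part of all revisions, the same 4 points allows a larger relative excess of loosening. A finding of non-inferiority could then be declared on very few events and would say little about whether the vitamin E insert loosens more often.

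**Working it through.** **1. Reproducing the plan's figure.** Inputs from section 10.1: control failure pc = 1 − 0.972 = 0.028; vitamin E failure pt = 1 − 0.977 = 0.023; margin m = 0.04; alpha 5%; power 80%. The section does not say whether alpha is one-sided or two-sided. One-sided 5% with independent groups reproduces 152, whereas one-sided 2.5% gives 193.

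n = (z_alpha + z_power)² × [pc(1−pc) + pt(1−pt)] / (m + pc − pt)²

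= (1.6449 + 0.8416)² × [0.027216 + 0.022471] / 0.045² = 6.1827 × 0.049687 / 0.002025 = 151.7, which rounds up to 152.

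Power at 152 = Φ(0.045 / √(0.049687/152) − 1.6449) = Φ(0.844) = 80.1%. The calculation is correct for the inputs given.

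**2. The margin against the planned rates (documents only).** 0.04 / 0.028 = 1.43. The failure rate tolerated in the vitamin E group is 2.8% + 4% = 6.8%, or 6.8/2.8 = 2.4 times the control rate. If L is the loosening rate at the same time point, loosening revisions are a subset of these revisions. Then L ≤ 2.8%, and 4%/L is at least 1.43.

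**3. Illustration for loosening.** The documents give no loosening share, so shares of 75%, 50% and 20% of the 5-year rates are assumed in both groups. The margin stays at 4 points and alpha at one-sided 5%. The normal-approximation column uses the power formula from step 1. The exact column sums binomial probabilities over all outcomes for which a restricted-maximum-likelihood score test rejects.

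| Assumed share | pc | pt | Control events per 152 | Margin / pc | Power, normal approximation | Power, exact (score test) |
|---|---|---|---|---|---|---|
| 75% | 2.10% | 1.725% | 3.2 | 1.9 | 87% | 77% |
| 50% | 1.40% | 1.15% | 2.1 | 2.9 | 95% | 86% |
| 20% | 0.56% | 0.46% | 0.9 | 7.1 | >99% | 97% |

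For example, at 75%: Φ(0.04375 / √((0.020559 + 0.016952)/152) − 1.6449) = Φ(1.140) = 87%. The two power columns differ by up to 10 points, and at the 75% share they fall on opposite sides of 80%. With one to three expected events, the figure depends on the test.

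**4. If the margin were scaled to the event (also assumed).** With margins of 3, 2 and 0.8 points for the same shares, power at 152 is 69%, 54% and 29% by the normal approximation, and 59%, 42% and 11% by exact enumeration. Proportional scaling is only one possible choice; the protocol frames its 4% as an absolute difference.

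**5. Revision for any reason at longer follow-up.** If both 5-year rates grew by an assumed factor of 1.4 (7/5), to 3.92% and 3.22%, power at 152 by the step 1 formula would be 71%. At an assumed factor of 2 (5.6% and 4.6%) it would be 63%. The 80% therefore does not transfer automatically to this endpoint either.

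**The case against.** The strongest reply is that the study is a retrospective consecutive series, 152 is a minimum, and a rarer event at a fixed 4-point margin needs fewer implants. On that view nothing is lost. It is true that the mismatch does not show the study to be too small. A reader might infer that 152 is miscalculated or that the study is underpowered; the documents support neither. The arithmetic reproduces, and without a loosening rate the power could lie on either side of 80%. The opposite inference, that a rarer event comfortably lifts power above 80%, is also unsupported, since the exact figure at the 75% share is 77%. Nor does the retrospective design remove the issue, because the protocol states a formal non-inferiority objective, margin and power.

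A reader might also object that the control rate is borrowed from highly cross-linked inserts, whereas section 5 describes non-cross-linked ones. That does not carry weight: the 2.77% figure is for mobile inserts, is not described as cross-linked, and rounds to the same 2.8%.

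It might seem that 7 years of follow-up makes the event counts above lower bounds. That is not established. Enrolment requires consent and 7 years of follow-up, and the documents do not settle how many early failures, deaths or losses will be represented.

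One further objection stands and widens the remedy. Section 10.2 contains no non-inferiority test, so a better rate in section 10.1 would still give the power of an analysis that is not planned.

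**Conclusion.** The concern holds in this form: the stated 80% power is not established for aseptic loosening, and the 4-point margin is not justified for it. The size that rests on the documents alone is a margin 1.43 times the planned control failure rate, tolerating 6.8% against 2.8%. At the same time point it is larger still relative to any subset of those revisions. All figures specific to loosening rest on assumed shares and serve only to show how few events are likely (about 1 to 3 control events per 152) and how strongly power depends on the test and the margin. No corrected sample size can be derived from the documents. The data remain usable, and the point should be settled before analysis.

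**What to change.** Add to section 10.1 a statement such as: *The figures of 152 implants per group and 80% power were computed from 5-year revision rates not restricted by cause; they do not describe the aseptic-loosening endpoint.* Then take one of two routes.

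- **(a) Keep aseptic loosening as the primary comparison.** Give a sourced loosening rate at the analysis time point, justify a margin against it, and restate the power at the 152 minimum by a method suited to few events.
- **(b) Make revision for any reason the endpoint of the non-inferiority comparison.** Justify the margin and restate the power for its expected rate at 7 years or more. Report aseptic-loosening survival by group with its 95% confidence interval, and make no 4-point claim on it.

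Under either route, amend section 10.2 so that the primary analysis compares the confidence limit of the between-group difference in Kaplan-Meier survival, at a stated time point and confidence level, with the margin. A log-rank test at p < 0.05 does not test non-inferiority: a non-significant result is not evidence that the difference lies within 4 points.

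Cost: no new data are needed for (b), since form 7 already records whether and when an implant was revised. Both routes need an amendment approved by the Ethics Committee under section 14. Because the cohort is retrospective, the amendment should state that it was made without reference to outcomes by group. The restated power may fall below 80% under either route, and under (b) the endpoint is less specific to the insert.

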10.2 Outcome analysis

Cumulative survival is calculated according to the Kaplan-Meier method [21], indicating the 95% confidence interval. Descriptive analysis to summarize the data and study results will be carried out by calculating mean, standard deviation and range of minimum and maximum values for continuous variables and by number and percentage for dichotomous variables. Data distribution was tested for normality with Shapiro-Wilk and D'Agostino Pearson tests.

The analysis of survival rates with 95% confidence intervals of study group versus control group will be performed with logarithmic rank test placing statistical significance at a p-value < 0.05.

The analysis of the differences between the 2 groups regarding the continuous variables will be carried out with Student's t test, while Mann-Whitney U test was used when distribution resulted not normal. The analysis of differences in dichotomous variables will be carried out with Chi-Square or Fisher's Exact tests if at least one of the variables has a value ≤ 5 .

The analysis will be carried out with one of the most used statistical software for this type of analysis (GraphPad Prism 10.1.0 Software, Boston, MA, USA).

11. Ethical and regulatory considerations

This clinical investigation is conducted in compliance with the ethical principles set out in the Declaration of Helsinki [22].

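### The 152 per group gives 80% power only at one-sided 5%; the plan does not state the side, and a 95% interval for the difference would give about 70%

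*Combined protocol and SAP*

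**What the plan says.** Section 4.1 makes non-inferiority the primary objective: survival with the vitamin E insert "is not inferior to the survival of the prosthetic implant with conventional polyethylene".

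Section 10.1 chooses a "statistical test of non-inferiority for binary variables (failed implant vs survived implant) of 2 paired groups". Its inputs are "choosing a significance level (alpha) of 5%, a power of 80" per cent, "a survival rate of 97.2% for the control and 97.7% for the vitamin E group", "with 4% as margin of non-inferiority between both groups"; and "the calculation provides 152 implants per group". The section does not say whether alpha is one-sided or two-sided.

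Section 10.2 says: "Cumulative survival is calculated according to the Kaplan-Meier method [21], indicating the 95% confidence interval". For the comparison it adds: "The analysis of survival rates with 95% confidence intervals of study group versus control group will be performed with logarithmic rank test", with significance at p < 0.05. It mentions no one-sided test and no 90% interval, and it has no rule that sets an interval for the difference against the 4-point margin.

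**The concern.** The power of a non-inferiority study depends on the error level at which the margin is tested. A claim read from the limit of a two-sided 95% interval is a one-sided 2.5% test; one read from a 90% interval is a one-sided 5% test. If the sample size rests on one level and the conclusion is drawn at the other, the stated power does not belong to the decision being made.

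Two things are at stake. First, 95% is the only interval level the plan names, so a reader may expect 80% power from it. On the planning rates the chance of missing a true non-inferiority result would then be about 30%, not 20%. Second, with the level left open, the same data could clear the margin on a 90% interval and fail on a 95% interval, and the choice could be made after the results are known. The implants date from 2011 to 2015 (section 6) and the sponsor is responsible for the analysis (section 8.3), so a level fixed in advance has real value.

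**Working it through.** **Inputs, all from section 10.1.** Survival: control 0.972, vitamin E 0.977. Margin 0.04. Power 80%. Alpha 5%, side not stated. Planned size 152 per group.

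**Formula.** Unpooled normal approximation for two independent proportions (section 10.1 calls the groups paired, but this is the formula that returns its figure):

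n = (z_alpha + z_beta)² × [p_C(1 − p_C) + p_T(1 − p_T)] / (margin + p_T − p_C)²

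- Variance term: 0.972 × 0.028 + 0.977 × 0.023 = 0.027216 + 0.022471 = 0.049687.
- Distance from the margin: 0.04 + 0.005 = 0.045; squared, 0.002025.
- z_beta = 0.842 for 80% power.

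**Step 1: reproduce the plan's figure.** One-sided 5%, z_alpha = 1.645, so (1.645 + 0.842)² = 6.183. Then n = 6.183 × 0.049687 / 0.002025 = 151.7, rounded up to **152**. This is an exact match.

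**Step 2: the same calculation at the level of a two-sided 95% interval.** One-sided 2.5%, z_alpha = 1.960, so (1.960 + 0.842)² = 7.849. Then n = 7.849 × 0.049687 / 0.002025 = 192.6, rounded up to **193** per group, or 386 in total against 304.

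**Step 3: power at 152 per group.** The standard error is √(0.049687 / 152) = 0.01808, and 0.045 / 0.01808 = 2.489.

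- One-sided 5% (90% interval): Φ(2.489 − 1.645) = Φ(0.844) = **80.1%**.
- One-sided 2.5% (95% interval): Φ(2.489 − 1.960) = Φ(0.529) = **70.2%**.

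**Step 4: exact check.** Failures are few at these rates, so both binomials were enumerated at 152 per group. Power uses failure rates of 2.8% (control) and 2.3% (vitamin E). Actual error is taken at the margin, with 2.8% and 6.8%.

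| Rule | Nominal one-sided level | Power | Actual error at the margin |
|---|---|---|---|
| Wald interval | 5% | 82.1% | 6.6% |
| Wald interval | 2.5% | 69.7% | 3.3% |
| Score (Farrington-Manning) test | 5% | 71.7% | 4.9% |
| Score (Farrington-Manning) test | 2.5% | 58.4% | 2.0% |

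The enumeration supports the normal approximation for the Wald rule. It also shows that this rule exceeds its nominal error at that point, and that the score test, which stays within it there, has lower power at either level.

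**Step 5: what these figures do not cover.** The log-rank test at p < 0.05 is a test of difference. As a rough guide, a two-sided test of 97.2% against 97.7% with 152 per group has about 5% power. Neither 80% nor 70% describes it.

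**The case against.** The best defence is that nothing in section 10.1 is miscalculated. A non-inferiority test looks in one direction by construction, so spending the whole 5% on one side is a natural reading, and 152 then follows exactly. The documents set no 2.5% requirement. This stands: a reader might infer that the stated 80% is an arithmetic error, and it is not. What is missing is the statement of the side and a matching level in the analysis.

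A second objection is that section 10.2 never promises to judge non-inferiority on a 95% interval. Its intervals belong to the survival estimates, and its p < 0.05 belongs to the log-rank test. This stands too. A reader might infer that the planned analysis as written has 70% power; the documents do not support that, because the interval for the difference to which 70% would apply is not defined. The figure is conditional. The condition is still a likely one, since 95% is the only interval level the plan offers for whatever margin comparison is eventually made.

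Third, 152 is a floor (sections 6.1 and 6.2 say at least that many knees), so a larger series would have more power. That is correct and limits the consequence, but it does not settle the level.

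Finally, the absence of any test against the margin is the larger gap. Agreed, but adding one still requires a level, and section 10.1's figure and section 10.2's intervals point to different ones.

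**Conclusion.** The point holds as a mismatch of error level, not as a wrong sum. The 152 per group with 80% power is valid only at one-sided 5%, which pairs with a two-sided 90% interval; neither section says so. If non-inferiority is judged on a two-sided 95% interval for the difference in survival, power at 152 is about 70%, roughly 10 points below the stated figure, and 193 per group would be needed for 80%.

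These figures assume the plan's own survival rates and margin, a binary outcome in two independent groups, the unpooled normal approximation, exactly 152 per group and no loss to follow-up. With the score test at 152 the power is about 72% at one-sided 5% and 58% at one-sided 2.5%, so 70% is not a pessimistic figure for a 95% interval.

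**What to change.** In section 10.1, state that 152 per group with 80% power was calculated at one-sided alpha of 5%. In section 10.2, define the interval for the between-group difference in survival that will be compared with the 4-point margin, including how it is calculated. Then use one level in both sections:

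- **Two-sided 90% interval (one-sided 5%).** The 152 per group and power of about 80% stand. The cost is a less strict interval, which should be justified.
- **Two-sided 95% interval (one-sided 2.5%).** Give that level in section 10.1 and restate the power of 152 per group as about 70%, noting that 80% would need 193. The cost is a less favourable stated power.

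If a score-based interval is chosen, quote the power for that method (about 72% or 58%). Neither option needs added patients. Because 152 is a minimum, power can be restated for the number actually included. The level and the interval should be fixed before the groups are compared.

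### Section 10.1 pairs 5% alpha with 80% power at 152 implants per group, but at the plan's own rates the two do not hold together: the test implied by the sizing has about 6.6% error, and a score test near 5% has about 72% power

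*Combined protocol and SAP*

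**What the plan says.** Section 4.1 makes non-inferiority of implant survival the primary objective, with revision for aseptic loosening as the failure event.

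Section 10.1 sizes the groups with a "statistical test of non-inferiority for binary variables (failed implant vs survived implant) of 2 paired groups". Alpha is set at 5% and power at 80%, and the planning rates are given as "a survival rate of 97.2% for the control and 97.7% for the vitamin E group". The conclusion reads: "with 4% as margin of non-inferiority between both groups, the calculation provides 152 implants per group". No formula is named and the sidedness of alpha is not stated; a web calculator is linked. The rates come from registry cumulative revision percentages at 5 years.

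The Synopsis and sections 6.1 and 6.2 treat 152 per group as a minimum, drawn from a consecutive series operated on from 2011 to 2015.

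Section 10.2 plans Kaplan-Meier estimates with 95% confidence intervals and a log-rank test at p < 0.05. It names no non-inferiority test and no confidence-limit rule against the 4-point margin. For dichotomous variables it moves from Chi-Square to Fisher's exact test when a value is 5 or less.

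**The concern.** The alpha and power in section 10.1 are the only operating characteristics given for the primary objective. They come from a large-sample formula applied where fewer than five failures per group are expected. Section 10.2 already avoids large-sample tests at such counts for other dichotomous comparisons, but the sizing does not.

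If the margin were tested in the way the sizing implies, an insert truly 4 points worse would be called non-inferior more often than 5% of the time. If it were tested with a method that holds close to 5%, the power at the planning rates would be below the stated 80%.

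**Working it through.** **Inputs, all from section 10.1:** control failure 1 - 0.972 = 0.028; vitamin E failure 1 - 0.977 = 0.023; margin 0.04 (absolute); alpha 5%; power 80%; 152 per group.

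**Step 1. Reproduce the plan's figure.** Unpooled normal approximation, two independent groups, one-sided 5%:

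n = (z₀.₉₅ + z₀.₈₀)² × [p_C(1 - p_C) + p_E(1 - p_E)] / (margin + assumed advantage)²

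- (1.645 + 0.842)² = 6.183
- 0.972 × 0.028 + 0.977 × 0.023 = 0.027216 + 0.022471 = 0.049687
- (0.04 + 0.005)² = 0.002025
- n = 6.183 × 0.049687 / 0.002025 = 151.7, rounded up to **152**

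The same formula at one-sided 2.5% gives 193. The asymptotic score formula at one-sided 5% gives 194. The match therefore points to the unpooled formula at one-sided 5%, although the protocol states neither.

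**Step 2. Expected failures.** 152 × 0.028 = 4.26 (control) and 152 × 0.023 = 3.50 (vitamin E).

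**Step 3. Exact operating characteristics at 152 per group.** The failure counts are taken as independent binomials and the probabilities of all count pairs that declare non-inferiority are summed (cutoff z = 1.645). Power is taken at failure rates of 2.8% (control) and 2.3% (vitamin E). Error is taken at the margin, 2.8% and 6.8%.

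| Rule | Error at the margin | Power |
|---|---|---|
| Unpooled Wald | 6.6% | 82.1% |
| Newcombe interval | 5.2% | 75.2% |
| Farrington-Manning score | 4.9% | 71.7% |

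None of the three has both an error of at most 5% and a power of at least 80%. The score test falls short by 80 - 71.7 = 8.3 points.

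**Step 4. Group size at which the score test reaches about 80%.** Exact power is 74.2% at 160, 77.2% at 170, 80.5% at 175, 80.0% at 180 and 80.6% at 185. The sequence is uneven because the counts are discrete. About 175-180 per group is a fair summary, which is 23 to 28 more than 152.

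**Step 5. Dependence on the failure rate.** The documents give no failure rate for aseptic loosening. The 0.5% and 1% rows below are assumptions.

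| Control failure | Wald error (vitamin E 4 points worse) | Score error (vitamin E 4 points worse) | Score power |
|---|---|---|---|
| 0.5% | 10.4% | 4.1% | 96.5% (0.5% in both groups) |
| 1% | 8.9% | 3.9% | 86.6% (1% in both groups) |
| 2.8% | 6.6% | 4.9% | 71.7% (vitamin E 2.3%) |

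At lower rates the score test's power shortfall disappears, while the Wald test's excess error grows.

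**The case against.** **The protocol's arithmetic is not wrong.** Its inputs return 152 by a conventional formula, and alpha and power are commonly quoted as nominal values. That stands. The point is that these nominal values are poor approximations at about four failures per group.

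**No Wald test is planned.** A reader might infer that the planned analysis has a 6.6% false non-inferiority rate. The documents do not support this: section 10.2 specifies only a log-rank difference test, so the error of a non-inferiority conclusion under the written analysis is not defined. The 6.6% belongs to the test that the sizing implies.

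**A valid test need not miss 80%.** A reader might infer that any valid test would fail more often than stated. That holds at the planning rates only. Revision for aseptic loosening is narrower than revision for any reason; if its true rate is 0.5-1% in both groups, the score test has about 96% to 87% power at 152.

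**152 is a floor.** The consecutive series may supply more knees, and about 175 per group would be enough at the planning rates. The documents therefore do not establish that the completed study will be underpowered.

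**The score test is not perfect either.** Its error reaches 5.5% at a control failure rate of 0%. Setting the cutoff so that the error stays at or below 5% over control rates of 0-25% lowers power slightly further, to 70.6%. A binary test also ignores censoring, which the Kaplan-Meier analysis is there to handle. Both limits should be stated, but neither restores the printed pair of 5% and 80%.

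**The word paired.** Nothing in the design pairs knees, so the word does not fit. It might be read as invalidating the sample size. It does not: with independent pairs the variance is the same, and 152 is unchanged.

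**Conclusion.** The point holds in a limited form. At the plan's own rates, margin and minimum group size, one-sided 5% error and 80% power do not hold together. The unpooled test behind the 152 delivers the power (82.1%) with an error of 6.6%. The score test delivers the error (4.9%) with a power of 71.7%.

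This rests on the following assumptions:
- the formula and the one-sided alpha are inferred from the match at 151.7;
- the true failure rates are 2.8% and 2.3%;
- every implant has a complete binary outcome;
- knees are independent, so bilateral implants, deaths and losses to follow-up would shift the figures.

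The discrepancy is moderate. It is a misstated operating characteristic of the primary objective that is cheap to correct. It does not show that the study must enrol more implants.

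**What to change.** **Section 10.1.** Restate the result along these lines: at the minimum of 152 implants per group, survival of 97.2% versus 97.7%, a 4-point margin and one-sided 5%, a score test for two independent groups has about 72% power (about 80% at 175-180 per group), assuming complete binary outcomes and independent knees.

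**Section 10.2.** Add that any comparison of failed/survived proportions with the 4-point margin uses the score limit (Farrington-Manning or Miettinen-Nurminen) and not the unpooled Wald limit.

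**Editorial.** Delete the word paired in 10.1. This changes no number.

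**Cost.** The stated power becomes less favourable, and the score limit may need software other than the package named in 10.2. No extra implants, visits or data are required.
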